## 1 INTRODUCTION

B. Braun Medical Inc. (B. Braun) is committed to enhancing clinical outcomes while managing workflow efficiencies. B. Braun leads the way in developing infusion therapy and pain management products and services that meet the highest standards for quality, safety, efficiency and sustainability.

Peripheral intravenous catheters (PIVCs) are used to deliver medication and fluids directly into the bloodstream. The placement of PIVCs is the most common invasive hospital procedure. In the United States (US) alone, more than 300 million PIVCs are sold each year and 60% to 90% of hospitalized patients require an IV catheter (Helm, 2015). Despite the large medical demand for PIVCs, there is a high failure rate and large cost associated with replacing the catheter due to complications, not counting the need to perform unnecessary PIVC insertions.

The Centers for Disease Control and Prevention (CDC) recommends rotating the PIVC site at 72 to 96-hour intervals to reduce the risk of infection and patient discomfort associated with phlebitis (O'Grady, 2002). However, typical catheter dwell times range from only 1.9 to 2.5 days (Powell, 2008; Royer, 2003; Sheppard, 1999). Failures, which occur in anywhere from 35% to 70% of PIVCs, take the forms of phlebitis, infiltration, occlusion/mechanical failure, dislodgment, and infection (Helm, 2015; Maki, 1991; Shears, 2006). A PIVC failure is considered to have occurred when the PIVC stops working safely before the end of the 72 to 96-hour limit or before the end of its intended dwell time (PIVC is no longer needed). These failures are associated with many factors, including the products used and the expertise of the clinician inserting and maintaining the PIVC, and add to the costs of intravenous (IV) therapy (Helm, 2015).

While the initial cost of inserting a PIVC in the US is roughly between \$28 and \$35 for “first-stick” insertions, the costs of identifying, inserting, and removing a PIVC is repeated each time a failed catheter is replaced (Helm, 2015; Rickard, 2012; Webster, 2008). Additional costs come from treating the PIVC complications such as bleeding, hematoma formation, infusate extravasation, thrombophlebitis, and catheter-related bloodstream infection (Smith, 1998; Greig, 2002; Doellman, 2009; Hollenbeak, 2012).

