### 12.2 Statistical Analyses for Secondary Endpoints

Standard statistical methods will be utilized in this study to analyze all data. Secondary endpoints that measure rates (e.g., first stick success) will be tested for significance using a binomial test (such as Fisher's exact test). Continuous endpoints will be tested for significance using standard parametric tests (such as Student's t-test), or non-parametric equivalent (such as Wilcoxon signed rank test) if parametric methods are found to be inappropriate.

Indwell Times: The source data are the indwell times measured for all catheters (e.g., catheter withdrawn due to complications, end of medical treatment, routine catheter change, end of treatment or voluntary withdrawal of subject from study). The indwell time is calculated from the time of catheter insertion until the time of catheter removal for any reason. In the event the subject or his/her LAR withdraws consent or is withdrawn by the PI, for any reason, and the catheter is still in place, the date and time of withdrawal will be used as a surrogate for the date and time of removal.

A survival analysis will be performed to further understand the difference in indwell times. A catheter will be considered to have been a failure/event if it is removed due to any

complication or failure of the unit. It will be considered censored/non-event if it is removed as it is no longer needed, i.e., the condition improves or the subject is discharged from the hospital.

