### **9.4. Secondary Endpoint Analyses**

Secondary endpoints that measure rates (e.g., first stick success and the rate of insertion of a Peripherally Inserted Central Catheter (PICC) or Midline Catheter) will be tested for significance between Stages 1 and 4 using a logistics regression while controlling the baseline characteristics such as years of nursing experience.

Both Indwell Times and Impact of using B. Braun PA on the healthcare costs associated with PIVC use will be compared between Stage 1 and Stage 4 using standard parametric tests (such as Student's t-test) or a non-parametric equivalent (such as Wilcoxon signed rank test) if parametric methods are found to be inappropriate. Appropriate regression models will likely be used to estimate the differences while controlling the baseline characteristics such as years of nursing experience.

A survival analysis by Kaplan Meier Curves between Stage 1 and Stage 4 will be performed to further understand the difference in time to any complication or failure of the unit. A catheter will be considered to have been a failure/event if it is removed due to any complication or failure of the device. It will be considered censored/non-event if it is removed as it is no longer

needed by the end of Stage 1 or Stage 4, i.e., the condition improves, or the subject is discharged from the hospital.

All secondary endpoint analyses will be performed in the MITT Population.

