## **16. FIGURES TO BE GENERATED**

Figure 16.1 Summary of Kaplan-Meier of onset of complication

– MITT Population

Figure 16.2 Summary of Kaplan-Meier of onset of Adverse Events

– MITT Population

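### The planned Kaplan-Meier curve censors catheters taken out at end of need, which is a competing event; read as a proportion, the curve is too high for its own event

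*SAP*

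**What the plan says.** SAP 9.4 defines the event: "A catheter will be considered to have been a failure/event if it is removed due to any complication or failure of the device". The censoring rule comes next: "It will be considered censored/non-event if it is removed as it is no longer". The rest of that sentence completes the thought of end of need, ties it to the close of a stage, and gives improvement or discharge as the reasons. Protocol 12.2 has the same rule: "It will be considered censored/non-event if it is removed as it is no longer needed".

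The purpose is worded differently in the two documents. The SAP wants the curves "to further understand the difference in time to any complication or failure of the unit"; the protocol says "A survival analysis will be performed to further understand the difference in indwell times".

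The SAP's list of figures includes "Figure 16.1 Summary of Kaplan-Meier of onset of complication", in the MITT population. Onset of a complication is not the event defined in 9.4, which is removal.

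The primary endpoint (SAP 6.3.1, Protocol 12.1) counts any complication. Protocol 12.1 records removal because of a complication as a separate yes/no item.

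SAP 10 states that the study ended before Stage 2 and that Stage 4 analyses will not be done. Figure 16.1 is still listed in that SAP. Neither document mentions competing risks or cumulative incidence.

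**The concern.** Kaplan-Meier censoring assumes that a censored unit remains at risk and has the same future hazard as those still under observation. Neither holds for a catheter taken out because therapy is over. It is no longer at risk, and the patients who improved or went home may differ from those still on infusion. One minus Kaplan-Meier then describes a hypothetical setting in which no catheter is ever removed for lack of need. It does not describe the share of catheters that actually had the event.

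The protocol's Introduction treats a catheter that works until it is no longer needed as not having failed. The curve treats the same catheter as one whose failure was merely not observed.

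At stake is how the remaining Stage 1 figure is read. A reader looking up 48, 72 or 96 hours will probably take the height of the curve as the proportion of catheters with the event by then. Nothing in the SAP warns against this.

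**Working it through.** The documents give no numerical result for the Kaplan-Meier analysis, so there is no planned figure to reproduce. The check sets one minus Kaplan-Meier beside the cumulative incidence for the same event.

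**Inputs**
- Mean dwell *m*: the Protocol Introduction says "typical catheter dwell times range from only 1.9 to 2.5 days", that is 45.6 to 60 h. Treating this typical range as a mean is an assumption.
- Share of catheters that end in the event, *p*: 50%, from the Stage 1 rate in SAP 9.1. That rate is for any complication; using it as the share removed for a complication is an assumption. The range 35% to 70% comes from the failure rates in the Protocol Introduction.
- Constant hazards for both kinds of removal: an assumption, varied below.

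**Formulas.** The event hazard is *a* = *p*/*m* and the total hazard is 1/*m*.
- One minus Kaplan-Meier at time *t*: 1 − exp(−*a t*)
- Cumulative incidence at time *t*: *p* × [1 − exp(−*t*/*m*)]

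**Example**, *p* = 0.5, *m* = 60 h, *t* = 96 h: 1 − exp(−0.5 × 96/60) = 1 − exp(−0.8) = 55.1%. Cumulative incidence: 0.5 × [1 − exp(−1.6)] = 39.9%.

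**Results for *p* = 50%** (the first value in each pair is for *m* = 60 h, the second for *m* = 45.6 h)

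| Time | 1 − Kaplan-Meier | Cumulative incidence | Gap, points |
|---|---|---|---|
| 48 h | 33.0-40.9% | 27.5-32.5% | about 5 to 8 |
| 72 h | 45.1-54.6% | 34.9-39.7% | about 10 to 15 |
| 96 h | 55.1-65.1% | 39.9-43.9% | about 15 to 21 |

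**Other shares at 96 h.** *p* = 35%: 42.9-52.1% against 27.9-30.7%. *p* = 70%: 67.4-77.1% against 55.9-61.5%.

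**End of follow-up.** Simulation with 316 catheters, 1,000 runs, *p* = 50% and mean dwell 52.8 h (the midpoint of 45.6 and 60) puts one minus Kaplan-Meier near 97% once every catheter is out. The cumulative incidence ends at the crude 50%.

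**Hazard shape.** Subjects must be expected to need a catheter for at least 48 h, so end-of-need removals may cluster later than a constant hazard implies. Keeping *p* = 50% and *m* at 45.6 to 60 h, with a constant event hazard and Weibull end-of-need times of shape 2 to 3, the gap is about 1 to 4 points at 48 h and 8 to 17 points at 96 h. If the event hazard also rises (Weibull shape 1.5), the gap at 96 h is about 13 to 26 points.

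**Against the primary rate.** With *p* = 50% and *m* = 52.8 h, one minus Kaplan-Meier is 36.5% at 48 h, 49.4% at 72 h and 59.7% at 96 h: below, about equal to, and above a primary rate of 50%. If only 60% of complications lead to removal, the share removed is 0.5 × 0.6 = 0.3. The curve at 96 h is then 1 − exp(−0.3 × 96/52.8) = 42.0%, below the primary 50%. It is still too high for its own event, whose cumulative incidence is 0.3 × [1 − exp(−96/52.8)] = 25.1%.

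**The case against.** The strongest defence is that the SAP never says the curve estimates a proportion. Its stated purpose is a difference in time to failure, and censoring end-of-need removals is a recognised cause-specific way to compare failure between two stages. The proportion is reported separately in Tables 14.4.1 and 14.4.2. This would carry weight if Stage 4 existed. With no Stage 4 analysis there is nothing to compare, and a single descriptive curve is most naturally read as a proportion. What stands is that Kaplan-Meier is not invalid in itself and may be kept as a labelled supportive display.

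It also stands that the size depends on the model: at 48 h the gap may be only a point or so. The analysis is secondary and descriptive, and no decision rests on it.

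A reader might go further and infer that the curve must contradict the primary table, or climb far above the crude Stage 1 rate. The documents do not support that. The primary analysis counts any complication; the 9.4 event is removal for a complication or device failure; Figure 16.1 names onset of complication. The MITT population also includes unsuccessful attempts, which have no dwell time, so the table and the curve may not share a denominator. Even when the shares are taken as equal, the curve lies below 50% at 48 h and on either side of it at 72 h.

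**Conclusion.** The point holds in this form: removal at end of need is a competing event, the plan censors it, and nothing elsewhere in either document repairs this. Read as the proportion of catheters with the event, one minus Kaplan-Meier is too high for whichever event is finally chosen. Under the constant-hazard illustration the excess is roughly 5 to 8 points at 48 h and 15 to 21 points at 96 h for a 50% event share.

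The direction of the excess for a given event does not depend on those assumptions; its size does. It rests on the assumed dwell, hazard shapes and event share, and the last depends on how many complications lead to removal. No fixed relation to Table 14.4.1 can be claimed. The change should be made, because the Stage 1 figure is easily misread, but no primary conclusion turns on it.

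**What to change.** 1. Reconcile the event in Figure 16.1 (onset of complication) with the event in SAP 9.4 (removal for a complication or device failure), and state one definition.
2. Make the Aalen-Johansen cumulative incidence of that event the main curve. Treat removal for any other reason as the competing event: end of need, discharge, or routine change. Protocol 12.2 lists routine change as a reason for removal, but the censoring rule does not classify it.
3. Censor only catheters still in place at withdrawal or study closure.
4. If a Kaplan-Meier curve is kept as a supportive cause-specific display, label it as not estimating the observed proportion. Note beside the figure that its event differs from that in Table 14.4.1 if that remains so.

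The cost is slightly more programming and one more definition in the SAP. No new data are needed: Protocol 6.1 already records dwell time and reason for removal. If onset is chosen as the event, its timing would come from the complication and daily examination entries.

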## 9.5. Safety Analyses

### 9.5.1. Adverse Events

For adverse event (AE) analyses, summary tables and/or listings will be provided for all AEs and severe adverse events (SAEs), respectively, in terms of event category by MedDRA coding for Stage 1 and Stage 4. In addition, both AEs and SAEs, respectively, will be summarized for Stage 1 and Stage 4 in terms of relationship to the procedure, to the device, and severity. Except where indicated, if a subject reports the same AE more than once, or reports the same AE on multiple occasions, the most severe AE will be presented when calculating the number and percentage of subjects with that particular event. AE outcomes will be assessed descriptively.

A descriptive line listing of each AE by subject also will be provided.

All safety analysis will be based on MITT Population, which includes only subjects in whom a procedure is attempted after enrollment.

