**Table 3: Classification of Adverse Events by Severity**

Mild: An event that is easily tolerated by the patient, causing minimal discomfort and not interfering with everyday activities.
Moderate: An event that is sufficiently discomforting to interfere with normal everyday activities.
Severe: An event that prevents normal everyday activities.

When changes in the severity of an AE occur more frequently than once a day, the maximum severity for the event should be noted. If the severity category changes over a number of days, then those changes should be recorded separately (with distinct onset dates).

An Adverse Device Effect (ADE) is an AE determined to be related to the use of the investigational device.

Specific guidelines for classifying AEs by relationship are provided below:

Definite – The adverse event is clearly related to the study device: the event has a temporal relationship to the study device, follows a known pattern of response, or is otherwise logically related to the study device, and no alternative cause is present.

Probable – The adverse event is likely related to the study device: the event has a temporal relationship to the study device, follows a known or suspected pattern of response, or is otherwise logically related to the study device, but an alternative cause may be present.

Possible – The adverse event is unlikely related to the study device: the event does not follow a clear temporal relationship to the study device or does not follow a

known pattern of response, or is otherwise possibly to be due to the subject's clinical state or other modes of therapy.

In some cases, the adverse event may not be adequately assessed because information is insufficient or contradictory and/or the data cannot be verified or supplemented. Maximum effort will be made to define and categorize the event and avoid these situations. If relatedness remains uncertain, then classify the event as "possible".

Unlikely – The adverse event can be reasonably explained by another cause and/or the relationship with the use of the device seems not relevant, but additional information may be obtained.

Not Related – The adverse event is clearly not related to the study device: the event has no temporal or other relationship to the administration of the investigational device follows no known or suspected pattern of response, and an alternative cause is present.

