## **11.2 Serious Adverse Events and Serious Adverse Device Effects**

An AE is considered "serious" if in the view of either the Investigator or Sponsor, it meets 1 or more of the following criteria:

- led to death,
- led to serious deterioration in the health of the subject, that either resulted in
- a life-threatening illness or injury, or
- a permanent impairment of a body structure or a body function, or
- in-patient or prolonged hospitalization, or
- medical or surgical intervention to prevent life-threatening illness or injury or permanent impairment to a body structure or a body function, or
- led to fetal distress, fetal death or a congenital abnormality or birth defect

A serious ADE is an Adverse Device Effect that has resulted in any of the consequences characteristic of an SAE.

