### 3. LIST OF ABBREVIATIONS AND DEFINITIONS OF TERMS

Abbreviation	Definition
AE	Adverse Event
B. Braun	B. Braun Medical Inc.
CP	Conditional Power
CRBSI	Catheter Related Bloodstream Infection
CRF	Case Report Form
CSR	Clinical Study Report
ED	Emergency Department
EDC	Electronic Data Capture
FDA	Food and Drug Administration
GCP	Good Clinical Practice
ICF	Informed Consent Form
ICH	International Conference on Harmonization
ITT	Intent to Treat
IRB	Institutional Review Board
ISO	International Organization for Standardization
LAR	Legally Authorized Representative
MITT	Modified Intent to Treat
PA	Peripheral Advantage
PICC	Peripherally Inserted Central Catheter
PIVC	Peripheral Intravenous Catheter
PP	Per Protocol
RN	Registered Nurse
SAE	Serious Adverse Event
SAP	Statistical Analysis Plan
SAS	Statistical Analysis System
SD	Standard Deviation
SOP	Standard Operating Procedure
US	United States
WHO	World Health Organization

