## 8.2. Protocol Deviations

A study deviation is defined as an instance(s) of failure to follow, intentionally or unintentionally, the requirements of the study protocol, applicable laws or regulations, or the Investigator Agreement. No deviation from the protocol will be implemented by an Investigator without the prior review and approval by the sponsor. Such approval will be documented in writing and maintained in the study files. The Investigator must document and notify the sponsor of any deviation from the study protocol no later than five (5) working days after becoming aware of the deviation. Deviations to the protocol will be reported by the site to their Institutional Review Board (IRB), as required.

Major deviations include those that involve the primary endpoint, the informed consent process and the inclusion/exclusion criteria of the study, or any deviation that involves or leads to a serious adverse event in a study participant. The protocol deviations classified as Major include, at a minimum:

- Date and time of insertion/removal not recorded
- Informed consent
- Inclusion/Exclusion
- Failure to record daily observation of catheter
- Failure to record reason for catheter withdrawal

Under certain circumstances, deviations from the study protocol to protect the rights, safety and well-being of human subjects may occur. Such deviations shall be documented in writing and reported to the Sponsor and the IRB, if required, as soon as possible, and no later than five (5) working days.

Subject specific deviations will be reported on the Protocol Deviation CRF. Investigators will adhere to procedures for reporting study deviations to their IRB as required. Deviations from the clinical protocol will be reviewed and evaluated by the sponsor on an ongoing basis and, as necessary, appropriate corrective actions put into place.

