## 14. STATISTICAL TABLES TO BE GENERATED

Table 14.1 Patient Disposition -ITT Population

Table 14.2.1 Demographics for Nurses - ITT Population

Table 14.2.2 Demographics and Patient Characteristics - ITT Population

Table 14.3 Summary of Daily Catheter Examination - MITT Population

Table 14.4.1 Summary of Primary Endpoint Analysis - MITT Population

Table 14.4.2 Summary of Primary Endpoint Analysis - PP Population

Table 14.5.1 Summary of Secondary Endpoint Analysis -MITT Population

Table 14.5.2 Summary of Secondary Efficacy Endpoint Analysis – Median Indwell time for Catheters -MITT Population

Table 14.5.3 Summary of Secondary Efficacy Endpoint Analysis – Median Indwell time for Catheters Subgroup Analysis - MITT Population

Table 14.6.1 Summary of Adverse Events -MITT Population

Table 14.6.2 Summary of Device and Procedure Related Adverse Events - MITT Population

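### SAP 9.5.1 spells SAE out as severe rather than serious, and no planned output title names serious events

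*SAP*

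**What the plan says.** SAP 9.5.1 sets out the adverse event analysis. It promises that "summary tables and/or listings will be provided for all AEs and severe adverse events (SAEs), respectively", by MedDRA category and by stage. It then asks for both AEs and SAEs to be summarised "in terms of relationship to the procedure, to the device, and severity", and adds a subject-level line listing of every adverse event.

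Elsewhere the SAP uses the other word. Its abbreviation list (Section 3) gives SAE as "Serious Adverse Event". Section 8.2 counts as major "any deviation that involves or leads to a serious adverse event in a study participant".

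The protocol keeps two scales apart. Table 3 grades intensity, with severe defined as "An event that prevents normal everyday activities". Section 11.2 calls an event serious when "in the view of either the Investigator or Sponsor, it meets 1 or more of the following criteria". The criteria that follow are outcomes: death, threat to life, lasting impairment, hospital admission or a longer stay, intervention to avert such harm, and fetal or congenital harm.

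SAP Section 14 has two adverse event tables: "Table 14.6.1 Summary of Adverse Events -MITT Population" and Table 14.6.2 for events related to the device or procedure. Section 15 has one adverse event listing, 15.4.

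**The concern.** Severe and serious overlap but are not the same set. The sentence that tells the programmer which events go into the SAE summary names the intensity grade, while the acronym beside it stands for the outcome-based concept everywhere else in both documents.

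Two examples show the consequence of a literal reading. A catheter infection that lengthens the hospital stay but is graded moderate is serious under protocol 11.2, yet would not be counted as an SAE. A painful infiltration graded severe that resolves without meeting any 11.2 criterion would be counted as one. The error can run in both directions, so even a plausible-looking total would not show that the right events had been counted.

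This matters for a safety report because readers take an SAE count to mean serious events. With the Stage 4 analyses dropped (SAP Section 10), the Stage 1 summary is the whole of the safety output.

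**Working it through.** No alpha, power, rate or sample size enters this point. The check is a comparison of wording and a count of output titles.

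**1. What each place says SAE means**

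| Place | Word or basis used |
|---|---|
| SAP 9.5.1 | severe |
| SAP Section 3, abbreviations | serious |
| SAP 8.2 | serious |
| Protocol abbreviation list and Section 10 | serious |
| Protocol 11.2 | serious, defined by outcome |
| Protocol Table 3 | severe, defined as the top intensity grade |

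SAP 9.5.1 stands alone. It conflicts with the SAP itself as well as with the protocol.

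**2. What 9.5.1 implies internally.** It asks for SAEs to be broken down by severity. If SAE meant severe, that breakdown would have a single category. It makes sense only if SAE means serious, so this is evidence of what was intended.

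**3. What a literal reading would do.** Classify events by seriousness (protocol 11.2) and by severity (Table 3):

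| | Graded severe | Graded mild or moderate |
|---|---|---|
| Meets an 11.2 criterion | a | b |
| Meets none | c | d |

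- Count under protocol 11.2: a + b
- Count under 9.5.1 read literally: a + c
- Difference in the total: (a + c) − (a + b) = c − b
- Events wrongly classified: b + c

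The total can agree (b = c) while b + c events are misclassified. The documents give no values for a, b, c or d.

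**4. Whether the output list settles it.** From SAP Sections 14 and 15: adverse event summary tables, 2 (14.6.1 and 14.6.2); adverse event listings, 1 (15.4); tables or listings whose title names serious events, 0. Section 9.5.1 allows tables or listings for SAEs, so some SAE output is promised, but the lists do not show where it will be.

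**5. Whether the correct information is collected.** Protocol 11.3 has the Investigator decide whether each event is an AE, SAE or ADE and record this on the eCRF. The seriousness determination therefore exists independently of the severity grade.

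**The case against.** The strongest reply is that this is one slip in expanding an acronym that the SAP defines correctly elsewhere. Much of that stands. The abbreviation list and Section 8.2 say serious, the severity breakdown in 9.5.1 points the same way, and no SAP text derives SAE status from the severity grade. Derivation rules are in separate specifications (SAP Section 13) that are not among the documents. A programmer who used the eCRF determination would produce the right summary.

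A reader might infer several stronger things that the documents do not support:

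- *That the SAP redefines SAE as severe.* It does not do so consistently; it contradicts itself.
- *That serious events would drop out of the report.* Any event in an MITT subject belongs in Table 14.6.1, Listing 15.4 and the by-subject listing whatever its label, and protocol 11.3 requires expedited SAE reporting regardless of grade.
- *That no serious-event output is planned.* Table 14.6.1 could carry SAE rows and Listing 15.4 a seriousness column. The table shells are not in the documents, so neither can be ruled out.
- *That protocol 12.3, which lets the SAP prevail over the protocol, makes severe the governing definition.* The SAP's own abbreviation list agrees with protocol 11.2, and SAP Section 10 declares no change to the planned analyses. The precedence rule does mean that protocol 11.2 cannot simply be assumed to correct the sentence.
- *That the effect can be sized from the planned Stage 1 complications, 316 × 50% = 158.* Recruitment stopped early, so 316 placements cannot be taken as reached. Complications are only assessed as potential AEs (protocol Section 8), and nothing in the documents gives the share that is severe but not serious.

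What the reply does not remove is that the wrong word sits in the operative sentence, the only one that specifies SAE summaries, and that neither the output titles nor a citation of protocol 11.2 corrects it.

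**Conclusion.** The point holds as a wording error in operative text. SAP 9.5.1 names the intensity grade where the outcome-based definition is meant, and the planned output titles leave the ambiguity open. Followed literally, it would misidentify which events are SAEs in both directions; the likely intention is serious.

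The reach is limited. Only descriptive Stage 1 safety output is affected, the primary and secondary endpoint analyses are untouched, and no event in an MITT subject would go unreported as an AE. The number of events misclassified, b + c above, cannot be estimated from the documents. It would be zero if the programming specifications already use the eCRF seriousness determination, which cannot be seen here. The correction is worth making because it is cheap and an SAE count should not depend on which section of the SAP the programmer follows.

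**What to change.** 1. In SAP 9.5.1, replace severe adverse events (SAEs) with serious adverse events (SAEs) as defined in protocol 11.2. State that SAE status is taken from the seriousness determination recorded on the eCRF and not from the severity grade.
2. Identify serious events in the named outputs: either a labelled SAE section in Table 14.6.1 or a separate SAE table for the MITT population, plus a seriousness column in Listing 15.4. Which table layout is used is a matter of preference.
3. Confirm that the programming specifications use the same source. If Stage 1 safety output has already been produced, check its SAE counts against the eCRF determinations.

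The cost is one changed sentence, one table section or table, and one listing column. No new data are needed, because protocol 11.3 already requires the determination to be recorded.
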